3.4.1.1. Primary Endpoints

- Incidence of MAAEs and SAEs through 1 week post final vaccine administration
- Incidence of MAAEs and SAEs through 30 days post final vaccine administration
- Incidence of MAAEs and SAEs through 6 months post final vaccine administration
- Incidence and severity of solicited local reactogenicity AEs through 1 week after each vaccine administration
- Incidence and severity of solicited systemic reactogenicity AEs through 1 week after each vaccine administration
- Incidence and severity of unsolicited AEs through 1 week post final vaccine administration

- Incidence and severity of unsolicited AEs through 30 days post final vaccine administration
- Incidence of abnormal changes of laboratory safety examinations
- Changes in vital signs

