6.3. Safety Assessments

All participants will be monitored for AEs during the study. Assessment of AEs will include the following parameters:

- All MAAEs and SAEs for 6 months after last vaccine administration (related MAAEs and SAEs at any time)
- Solicited local and systemic AEs via diary for 7 days after each vaccine administration (applicable to the phase 1 and phase 2 studies)
- Unsolicited AEs via diary from first dose of study treatment until 30 days after last vaccination (applicable to the phase 1 and phase 2 studies)
- Vital signs
- Body weight
- Physical examinations
- Hematology: CBC with differential
- Chemistry panel: Collection of whole blood for complete metabolic panel (CMP)
- Urinalysis: protein, glucose, and RBCs
- Pregnancy test.

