6.3.1. Solicited Local and Systemic Adverse Events

Solicited AEs will be captured at study visits and by a diary distributed to participants. Thermometers and rulers will be provided to participants for evaluating AEs. Text and/or phone reminders to complete the solicited AE diary may be provided to participants.

Solicited local AEs to be assessed include redness, firmness, swelling, pain or itching at the injection site, medication taken for pain after IM administration, tingling/numbness, and bleeding or bruising at the injection site after IM administration. Solicited systemic AEs to be assessed include chills, nausea, vomiting, diarrhea, headache, fatigue, myalgia, abdominal discomfort/pain, joint pain, and fever. The solicited AE diary may be either electronic diary (eDiary) or a paper diary, as available. A sample diary for collecting solicited AEs is provided in [Appendix 1](#).

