7.3. Definition of Serious Adverse Events

AEs and grading criteria listed below are consistent in definitions in 21 CFR 312.32. AEs can be further divided into solicited AEs and unsolicited AEs. Solicited AEs are those for which the study team will specifically query the participant whether they occurred. Unsolicited AEs are those events that the participant report occurring without being queried about the specific event.

An SAE is any AE that suggests a significant hazard or AE, whether or not considered to be related to study treatment. An SAE fulfills one or more of the following criteria:

- Results in death.
- Is life-threatening (ie, in the opinion of the Investigator, the participant is at immediate risk of death from the AE as it occurred).
- Requires in-subject hospitalization or prolongation of existing hospitalization (hospitalization is defined as an in-subject admission, regardless of length of stay).
- Results in persistent or significant disability or incapacity (a substantial disruption of the participant's ability to conduct normal life functions).
- Results in a congenital abnormality or birth defect.
- Is an important medical event that may jeopardize the participant or may require medical intervention to prevent one of the outcomes listed above. Important medical events are defined as those occurrences that may not be immediately life-threatening or result in death, hospitalization, or disability, but may jeopardize the participant or require medical or surgical intervention to prevent one of the other outcomes listed above. Medical and scientific judgment should be exercised in deciding whether such an AE should be considered serious.

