APPENDIX 1. SAMPLE DIARY FOR SOLICITED EVENTS

STUDY NUMBER*: _____

Patient Number*		Date of Vaccine Administration	/	/	/	*To be completed by the site		
-----------------	--	--------------------------------	---	---	---	------------------------------	--	--

Please answer all questions below daily for 7 days, beginning with day of treatment. Be sure to bring back this completed diary to your next clinic visit.

Intramuscular: Solicited local AEs	Instructions	Date / /						
1. Is there redness at the injection site?	Check:  Yes or  No If yes, measure longest diameter in cm	 Yes or  No _____ cm	 Yes or  No _____ cm	 Yes or  No _____ cm	 Yes or  No _____ cm	 Yes or  No _____ cm	 Yes or  No _____ cm	 Yes or  No _____ cm
2. Is there firmness at the injection site?	Check:  Yes or  No	 Yes or  No	 Yes or  No	 Yes or  No	 Yes or  No	 Yes or  No	 Yes or  No	 Yes or  No
3. Is there swelling at the injection site?	Check:  Yes or  No If yes, measure longest diameter in cm	 Yes or  No _____ cm	 Yes or  No _____ cm	 Yes or  No _____ cm	 Yes or  No _____ cm	 Yes or  No _____ cm	 Yes or  No _____ cm	 Yes or  No _____ cm

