APPENDIX 2. SAMPLE DIARY FOR UNSOLICITED EVENTS

STUDY NUMBER*: _____

Patient Number*	Date of Vaccine Administration	/ /	*To be completed by the site
-----------------	--------------------------------	-----	------------------------------

Please complete this diary every day beginning on the day you receive the first dose of study vaccine until 30 days after you receive the last dose of study vaccine. Each page has space for recording 7 days of information. You will be provided with enough pages to last until 30 days after you receive the last dose of study vaccine. Be sure to bring this diary each time you visit the clinic and refer to this diary when study personnel contact you by telephone for schedule safety follow up assessments.

Unsolicited AEs	Date / /						

Please describe any unusual feelings of discomfort, signs or symptoms that are not specified on the other daily diaries. If you do not experience these feelings, signs, or symptoms, please mark "no additional symptoms to report". For each separate sign and symptom you report in the diary, please note the following:
 
 • How intense it is, either Mild (no interference with activity), Moderate (some interference with activity), or Severe (significant; prevents daily activity) • How long it lasts • Any actions you took to manage the symptoms (for instance, taking medication) 							

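### Once the 7-day solicited diary ends, the sample unsolicited-event diary has no prompt for the listed symptoms, so the 30-day unsolicited-AE endpoint is at risk of under-recording

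*Combined protocol and SAP*

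**What the plan says.** Two sample diaries collect symptoms.

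- **Solicited diary (Appendix 1).** Participants are told: "Please answer all questions below daily for 7 days, beginning with day of treatment". It has 8 local and 10 systemic items. Section 6.3.1 gives the content: "Solicited systemic AEs to be assessed include chills, nausea, vomiting, diarrhea, headache, fatigue, myalgia, abdominal discomfort/pain, joint pain, and fever", with the local list opening "Solicited local AEs to be assessed include redness, firmness, swelling, pain or itching at the injection site". In phase 2 experimental arm 3, a second solicited diary is issued on day 29 (Table 10, footnote f).
- **Unsolicited diary (Appendix 2).** It is completed "beginning on the day you receive the first dose of study vaccine until 30 days after you receive the last dose of study vaccine". It asks for "signs or symptoms that are not specified on the other daily diaries", and gives a nothing-further-to-report entry for days without such symptoms. The instruction does not change when the solicited diary ends.

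Section 6.3 specifies collection of "Unsolicited AEs via diary from first dose of study treatment until 30 days after last vaccination". Section 7.3 defines the class by how the event is reported: "Unsolicited AEs are those events that the participant report occurring without being queried about the specific event". The endpoint served is "Incidence and severity of unsolicited AEs through 30 days post final vaccine administration", which is primary in phase 1 (Section 3.4.1.1) and secondary in phase 2 (Section 3.4.2.2.1).

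The diary is not the only route. Section 6.3.2 also captures unsolicited AEs at study visits. Section 7.4.3 has the investigator ask at each visit, for 30 days after the last dose, about AEs since the previous contact. Table 10 schedules in-office AE collection on days 1, 8, 22, 29 and 60, and a day-36 telephone call for arm 3.

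**The concern.** The exclusion in Appendix 2 makes sense while the solicited diary is also being filled in, because it avoids recording the same symptom twice. Once that diary stops, the exclusion has no counterpart. A headache or a delayed arm reaction on day 12 is on the solicited list, so a literal reader leaves it out of the unsolicited diary, and no other diary is open. The nothing-further-to-report entry can then make the day look event-free rather than blank.

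The symptoms affected are the common vaccine-type ones, over most of the 30-day window of a phase 1 primary endpoint. Late or persisting reactogenicity is what would be recorded least well. The same data feed safety oversight: under Section 7.8.2 the Safety Review Committee reviews treatment-related grade 3 or higher AEs after the 7-day period, and grade 3 unsolicited AEs count towards a pausing criterion. Contemporaneous entries cannot be recreated afterwards.

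The available text also does not say whether a listed symptom that starts after the 7 days is analysed as unsolicited, or how one still present when the 7 days end is carried forward.

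**Working it through.** The plan states no figure on this point, so there is none to reproduce. The check is a count of days.

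**Inputs**

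- Unsolicited diary: day of first dose to 30 days after last dose (Appendix 2).
- Solicited diary: 7 days, dose day included (Appendix 1).
- Dosing: day 1; day 1 and day 29 in arm 3 (Section 3.3.1).
- Contacts: clinic visits on days 8, 22, 29 and 60; day-36 call in arm 3 (Table 10).

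**Step 1. Days without a diary prompt** = unsolicited-diary days − solicited-diary days.

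| Group | Unsolicited diary | Solicited diary | No prompt | Share |
|---|---|---|---|---|
| Single dose (all of phase 1; phase 2 control, arms 1 and 2) | days 1–31 (31) | days 1–7 (7) | days 8–31: 31 − 7 = 24 | 24/31 = 77% |
| Arm 3 | days 1–59 (59) | days 1–7 and 29–35 (14) | days 8–28 and 36–59: 59 − 14 = 45 | 45/59 = 76% |

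**Step 2. Sensitivity to the 7-day wording.** Section 6.3 speaks of 7 days after each administration. Read as dose day plus 7 days, the solicited period is 8 days. The gap becomes 31 − 8 = 23 days (23/31 = 74%) for a single dose and 59 − 16 = 43 days (43/59 = 73%) in arm 3. The conclusion is the same.

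**Step 3. Recall that visits must cover** (nominal days)

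- Day 8 to day 22: 22 − 8 = 14 days.
- Day 22 to day 29: 7 days.
- Single dose, days 30–31: next contact is day 60, so 60 − 30 = 30 and 60 − 31 = 29 days back.
- Arm 3 after dose 2: day-36 call to day 60 = 24 days.

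Section 7.4.3 limits the all-AE inquiry to 30 days after the last dose: day 31 for a single dose, day 59 in arm 3. Nominal day 60 falls after both, although Table 10 does list in-office AE collection that day.

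**Step 4. Size of any under-recording.** Expected participants missed = n × p × (1 − c), where p is the share with a listed symptom only in the gap and c is the share recovered at visits. The documents give neither p nor c. As an assumption only, take p = 10–30%:

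| Visit capture c | Cohort of 10 | Arm of 30 |
|---|---|---|
| 0% | 1–3 | 3–9 |
| 80% | 0.2–0.6 | 0.6–1.8 |
| 100% | 0 | 0 |

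The range includes zero, so it illustrates a risk and does not estimate a bias.

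**The case against.** The best reply is that the diary is one of two required routes. Investigators ask about AEs at visits, including day 8, just after the first solicited diary ends, and a day-12 headache mentioned at day 22 would enter the endpoint. For single-dose participants the recall interval is 14 days, then 7; only days 30–31 wait until day 60. This stands, and it is why the point is a risk and not a demonstrated under-count. It does not close the gap. The diary is what is reviewed at visits, and participants are told to consult it during telephone contacts, so the visit inquiry leans in part on the same record. After arm 3's second dose the visit route is thin.

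Second, the exclusion might be read as referring only to diaries being completed at the same time, and both appendices are labelled samples. This stands too: the text is ambiguous and the issued version may differ. An instruction open to both readings should still be settled before use.

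Third, the consequences are bounded. Analyses are descriptive with no comparison of phase 2 arms (Section 8.3.1), the toxicity assessment period behind each cohort review is the 7 days that the solicited diary covers (Section 7.8.2), and medically attended and serious events are collected for 6 months (Section 6.3). What remains is mainly milder late symptoms. This lowers the priority but leaves the defect in place.

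**Conclusion.** The gap is in the text. If the Appendix 2 instruction is followed literally, the listed symptoms have no diary prompt on 24 of 31 days for single-dose participants and 45 of 59 days in arm 3, and their capture depends on recall at visits. The 30-day unsolicited-AE endpoint is at risk of under-recording by an amount the documents do not allow one to compute. This assumes that the issued diary matches the sample and that participants take the exclusion at face value.

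Three stronger readings are tempting and are not supported:

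- **That the endpoint is certainly under-counted.** Visit inquiry is a second route into it and could recover every event.
- **That events still present when the solicited diary ends lose their source for duration and end date.** Section 7.4.3 has the investigator record start and stop dates for all AEs, and Section 7.4.4 sets their follow-up.
- **That Appendix 2 contradicts Section 7.3.** The definition turns on how an event is reported, so a listed symptom volunteered after the solicited diary ends still qualifies as unsolicited. The diary instruction is incomplete; it does not conflict with the definition.

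This is a low-cost improvement to a safety endpoint, not a flaw that invalidates it.

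**What to change.** Change the Appendix 2 instruction along these lines: *During the 7 days when you also fill in the other diary, record here only symptoms that are not listed there. After those 7 days, record any symptom that starts or is still present, including those listed on the other diary.* In arm 3 the first sentence applies again for the 7 days from the second dose.

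Add to Section 6.3.2 that listed symptoms with onset after the 7-day period are analysed as unsolicited AEs, and that listed symptoms still present at its end stay classified as solicited, with their end date recorded.

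With this change, days without a diary prompt fall from 24 (45 in arm 3) to 0. The cost is one diary instruction, a classification rule in the protocol, slightly more diary entry, and slightly higher reported unsolicited-AE rates. Visits, dosing and sample size are untouched. If the issued diary already lifts the restriction after 7 days, only the Section 6.3.2 addition is needed.
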